## **6.12.2. Secondary Efficacy Analyses Subject to Type 1 Error Rate Control**

### **6.12.2.1. Mean Change in HbA1c from Baseline at the 52 Week Visit**

Noninferiority of 5 mg LY3198176 to insulin degludec will be conducted in a manner similar to Section 6.12.1. Assessment of Superiority of tirzepatide doses compared to insulin degludec will be conducted using the same statistical models as those used for evaluating the primary objective in Section 6.12.1. Decisions will be guided by the 2-sided p-values for mean comparisons between tirzepatide doses and insulin degludec (see details in Section 6.12.3).

### **6.12.2.2. Mean Change in Body Weight from Baseline at the 52 Week Visit**

The analysis for change in body weight from baseline (postbaseline – baseline) will be conducted in a manner similar to the primary analysis in Section 6.12.1. Baseline HbA1c concentration ( $\leq 8.5\%$ ,  $> 8.5\%$  [ $\leq 69$ ,  $> 69$  mmol/mol]) will be used as a fixed factor in place of baseline HbA1c as a covariate and baseline body weight will be used as an additional covariate in the statistical model. Least squares mean estimates of mean change in body weight from baseline will be plotted by nominal visit and by study treatment. For multiple imputation of missing values, if the imputed value of weight change from baseline is  $< -50$  kg or  $> 50$  kg, then that value will be set to  $-50$  kg or  $50$  kg, respectively, to avoid unrealistic imputed values.

### 6.12.2.3. Proportion of Patients Achieving HbA1c <7% at the 52 Week Visit

Analyses relative to the “efficacy” estimand for the endpoint at 52 weeks will be performed using the EAS with missing values imputed from an MMRM model and then dichotomized. The MMRM model includes treatment, country/pooled country, baseline concomitant oral antihyperglycemic medication use, visit, and treatment-by-visit interaction as fixed effects, and baseline HbA1c as a covariate. After dichotomizing continuous HbA1c, the data are analyzed using a logistic regression model with treatment, country/pooled country, and baseline concomitant oral antihyperglycemic medication use as fixed effects, and baseline HbA1c as a covariate. In addition, an analysis will be conducted utilizing data using the EAS from baseline through the 52-week visit with the aid of a longitudinal logistic regression with repeated measurements with country/pooled country, baseline concomitant oral antihyperglycemic medication use, treatment, visit, and treatment-by-visit interaction as fixed effects, and baseline HbA1c as a covariate. If the longitudinal logistic model does not converge due to a small number of events, logistic regression will be utilized to analyze the proportion of patients achieving HbA1c <7% at nominal visits.

[figure not shown]
Analyses relative to the “treatment-regimen” estimand will be conducted utilizing HbA1c data in the FAS at baseline and at the 52-week visit with the aid of a logistic regression with multiple imputation of missing HbA1c data at the 52-week visit (see Section 6.12.1.3 for details). Model terms will include treatment, country/pooled country, and baseline concomitant oral antihyperglycemic medication use as fixed effects, and baseline HbA1c as a covariate. Statistical inference over multiple imputations will be guided by Rubin (1987).

### 6.12.3. Type 1 Error Rate Control Strategy for Primary and Key Secondary Efficacy Analyses

Since they are intended for different purposes, no type 1 error rate adjustments will be made for conducting analyses relative to “efficacy” and “treatment-regimen” estimands. For analyses within each estimand, the type 1 error control strategy for evaluation of the primary and key secondary objectives is illustrated in [Figure GPGH.6.1](#).

1.  $H_{15,1}$ ,  $H_{15,2}$ , and  $H_{15,3}$  are evaluated hierarchically each at a 2-sided 0.025 significance level conditioned on successfully achieving the preceding objective. In parallel,
2.  $H_{10,1}$ ,  $H_{10,2}$ , and  $H_{10,3}$  are evaluated hierarchically each at a 2-sided 0.025 significance level conditioned on successfully achieving the preceding objective.
3.
  - a. If all objectives in #1 and #2 above are successfully established,  $H_{5,1}$ ,  $H_{5,2}$ , and  $H_{5,3}$  are evaluated hierarchically, each at a 2-sided 0.05 significance level.
  - b. If all objectives in only #1 or only #2 above are successfully established,  $H_{5,1}$ ,  $H_{5,2}$ , and  $H_{5,3}$  are evaluated hierarchically, each at a 2-sided 0.025 significance level.
4. If all objectives:  $H_{5,1}$ ,  $H_{5,2}$ , and  $H_{5,3}$  are successfully established and

- a. If all objectives in #1 and #2 above are successfully established, then  $H_{10,4}$ ,  $H_{15,4}$ , and  $H_{5,4}$  will be evaluated hierarchically each at a 2-sided 0.05 significance level conditioned on successfully achieving the preceding objective.
  - b. If all objectives in only #1 or only #2 above are successfully established, then  $H_{10,4}$ ,  $H_{15,4}$ , and  $H_{5,4}$  will be evaluated hierarchically each at a 2-sided 0.025 significance level conditioned on successfully achieving the preceding objective.
5. If all objectives in #3 and #4 above are successfully established, and at least 1 objective from #1 or #2 above is not successfully established, recycle 100% of the unused alpha back to #1 or #2 above.

**Figure GPGH.6.1. Type 1 error control strategy for primary and key secondary efficacy endpoints.**

### 6.12.4. Other Secondary and Exploratory Efficacy Analyses

Other secondary and exploratory efficacy measures will be summarized by treatment and nominal visit. Statistical analyses will be conducted in a manner similar to Sections 6.12.1 and 6.12.2, however missing data will not be imputed and assessments are not subject to type 1 error rate control.

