#### **6.4. Handling of Dropouts or Missing Data**

For the primary and key secondary efficacy endpoint analyses subject to type 1 error rate control, data for patients with missing values at the 52-week visit will be imputed based on the method described in Section 6.12.1.3. Unless specified otherwise, imputation of missing data will be limited to primary and key secondary efficacy endpoint analyses. Missing other secondary or exploratory efficacy parameter values and missing safety laboratory values will not be explicitly imputed.

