## **6.12. Efficacy Analyses**

For the Food and Drug Administration (FDA) and potentially for other regulatory agencies, all efficacy assessments will be guided by the “treatment-regimen” estimand conducted using the FAS. Assessment of the primary and secondary efficacy objectives subject to type 1 error rate control (key secondary) will be conducted with multiple imputation of missing data (see Section 6.12.1.3) at 52 weeks. Assessment of other efficacy objectives will be conducted without imputation of missing data. For publications and other purposes, the assessment of efficacy objectives will be guided by the “efficacy” estimand using the EAS without imputation of missing data.

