### **6.12.1.3. Methods for Multiple Imputations**

For efficacy analyses relative to the “treatment-regimen” estimand, missing HbA1c data at the 52-week visit will be imputed based on “retrieved dropouts,” defined as patients who had their HbA1c value measured at the 52-week visit in the same treatment arm who prematurely discontinued study drug. If the imputed value of HbA1c change from baseline is  $< -6.0\%$  or  $> 6.0\%$ , then that value will be set to  $-6.0\%$  or  $6.0\%$ , respectively, to avoid unrealistic imputed values.

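### For the treatment-regimen estimand, five Week 52 responder endpoints become complete-case analyses although the HbA1c and weight values behind them are already multiply imputed

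*SAP*

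**What the plan says.** SAP 6.12 has every efficacy assessment for the FDA follow the treatment-regimen estimand on the FAS. SAP 6.2 defines that estimand as efficacy regardless of adherence or rescue.

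Three sections then restrict imputation:
- SAP 6.4: "imputation of missing data will be limited to primary and key secondary efficacy endpoint analyses", and "Missing other secondary or exploratory efficacy parameter values and missing safety laboratory values will not be explicitly imputed".
- SAP 6.12: "Assessment of other efficacy objectives will be conducted without imputation of missing data".
- SAP 6.12.4: "Statistical analyses will be conducted in a manner similar to Sections 6.12.1 and 6.12.2, however missing data will not be imputed".

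The underlying Week 52 variables are imputed elsewhere:
- HbA1c, SAP 6.12.1.3: "missing HbA1c data at the 52-week visit will be imputed based on" retrieved dropouts, that is, patients in the same arm who stopped study drug early but still had a Week 52 value.
- Weight, SAP 6.12.2.2: the analysis follows the primary one, and limits are set on imputed values ("For multiple imputation of missing values, if the imputed value of weight change from baseline is" beyond 50 kg in either direction). SAP 6.4 applies the 6.12.1.3 method to all key secondary endpoints.
- HbA1c <7%, SAP 6.12.2.3: "logistic regression with multiple imputation of missing HbA1c data at the 52-week visit".

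Table GPGH.6.2 lists HbA1c ≤6.5%, HbA1c <5.7% and weight loss ≥5%, ≥10% and ≥15% as secondary superiority endpoints, each to be analysed like Section 6.12.2.3.

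**The concern.** HbA1c ≤6.5% and <5.7% are the same measurement as HbA1c <7% with a different cut-off. The weight-loss targets are cut-offs on a weight value that is also imputed for a key secondary endpoint.

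Take a patient with no Week 52 HbA1c. For the <7% target, the plan assumes that this patient resembles same-arm patients who stopped the drug. For the ≤6.5% target, it drops the patient, which amounts to assuming resemblance to all observed same-arm patients with similar covariates. No section explains the difference.

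Two things are at stake. An estimand defined regardless of adherence would be estimated only in patients who have a Week 52 value. And nested targets would be reported for different sets of patients, so a reader could not compare them directly.

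**Working it through.** **Is it complete-case?** Section 6.12.2.3 contains three methods. Two are written for the EAS: logistic regression after filling gaps from an MMRM, and longitudinal logistic regression. The third, for the treatment-regimen estimand, is logistic regression on FAS data at baseline and Week 52 with multiple imputation. Removing the imputation from the third leaves patients with an observed Week 52 value.

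**The plan's own figures.** The plan gives no responder rate, Week 52 missing rate or power for these endpoints. Its one computable design figure is the 90% power in SAP 5.2 for HbA1c change. With a net difference of 0.35 − 0.05 = 0.30, two-sided alpha 0.025, success on at least one dose, and correlation 0.5 between the two comparisons (which share the control arm), it reproduces:
- SD 1.1% and 355 × 0.72 = 255.6 per arm: 91.3%.
- SD 1.3% and 355 per arm: 91.1%.

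That figure does not involve the responder endpoints.

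**Size in one arm.** Let m be the share missing at Week 52, p_obs the observed response rate and p_imp the response rate among imputed values.
- Imputed rate = (1 − m) × p_obs + m × p_imp
- Complete-case rate − imputed rate = m × (p_obs − p_imp)

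All inputs below are assumptions.

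| m | p_obs | p_imp | Complete-case | Imputed | Difference (points) |
|---|---|---|---|---|---|
| 5% | 70% | 20% | 70.0% | 67.5% | +2.5 |
| 10% | 70% | 20% | 70.0% | 65.0% | +5.0 |
| 15% | 70% | 20% | 70.0% | 62.5% | +7.5 |
| 10% | 90% | 60% | 90.0% | 87.0% | +3.0 |
| 10% | 90% | 0% | 90.0% | 81.0% | +9.0 |
| 10% | 30% | 40% | 30.0% | 31.0% | −1.0 |
| 10% | 6% | 15% | 6.0% | 6.9% | −0.9 |

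The last two rows show the sign turning when imputed patients respond more often than observed ones. The last could describe weight loss on degludec.

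**Treatment difference.** Assume observed rates of 80% (tirzepatide) and 45% (degludec), so the complete-case difference is 35.0 points.

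| Missing, tirzepatide / degludec | p_imp, tirzepatide / degludec | Imputed rates | Imputed difference (points) |
|---|---|---|---|
| 10% / 10% | 30% / 30% | 75.0% − 43.5% | 31.5 |
| 15% / 5% | 30% / 30% | 72.5% − 44.25% | 28.3 |
| 5% / 15% | 30% / 30% | 77.5% − 42.75% | 34.8 |
| 5% / 15% | 40% / 20% | 78.0% − 41.25% | 36.8 |

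The complete-case difference is too large in the first three rows and too small in the fourth.

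**Order of nested rates.** The reported ≤6.5% rate (complete-case) exceeds the reported <7% rate (imputed) when the observed gap between the two is smaller than m × (p_obs − p_imp), with both rates taken for the <7% target. To judge how likely that is, assume 84% observed below 7.0%, 25% imputed, and a roughly normal Week 52 HbA1c. As a proxy for its SD take 1.1% to 1.3%, the SAP 5.2 values for change.
- SD 1.1%: 70.5% are at or below 6.5%, a gap of 13.5 points. Reversal needs m > 13.5 / 59 = 23%.
- SD 1.3%: 72.9% are at or below 6.5%, a gap of 11.1 points. Reversal needs m > 11.1 / 59 = 19%.

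**The case against.** **The rule is deliberate.** It is prespecified and stated consistently in three sections, and limiting imputation to the type 1 error-controlled endpoints is a recognisable choice. That is fair, and the rule is not a drafting slip. But the choice is not justified anywhere, and it costs consistency on variables that are imputed anyway.

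**Complete-case is inferred.** Table GPGH.6.2 only asks for a similar analysis, 6.12.2.3 also contains a longitudinal logistic model, and the SAP revision history links that model to the weight-loss targets. However, 6.12.2.3 specifies it for the EAS only, so complete-case remains the natural reading for the FAS.

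**Missingness may be small.** Protocol 8.1.1 keeps patients in follow-up after they stop the drug. Protocol Appendix 7 widens the Week 52 window and allows home visits, and SAP 6.12.1 accepts local-laboratory and unscheduled HbA1c. Some missing visits may be pandemic-related in patients still on drug. All this stands. The 28% in SAP 5.2 covers rescue or early discontinuation and is not a Week 52 missing rate.

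**Stronger readings.** A reader might infer that the reported rates are certainly inflated, or that a stricter target will be reported as met by more patients than a looser one. The documents support neither: they give no missing or response rates, the sign can reverse, and a reversed order would need unusual data. A reader might also extend the point to fasting glucose and SMBG. Table GPGH.6.2 sends those to all of Section 6.12.1, which includes the MMRM, so a complete-case Week 52 analysis is not established for them.

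**Conclusion.** The inconsistency holds: under the treatment-regimen estimand, the same missing Week 52 HbA1c or weight is imputed for some endpoints and dropped for others. This follows from the text and does not depend on the direction of any bias.

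The size rests on assumptions. On the 70%/20% case it is 2.5 to 7.5 points in an arm for 5% to 15% missing. Upward bias is probable in the tirzepatide arms if patients who stopped the drug respond less often. It is not assured elsewhere, and the treatment difference can move either way.

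The endpoints lie outside type 1 error control (SAP 6.6 and 6.12.4), so the primary and key secondary conclusions and the sample size are untouched. The change is worth making because it is nearly free.

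**What to change.** Amend SAP 6.4, 6.12 and 6.12.4 so that, for the treatment-regimen estimand:
- HbA1c ≤6.5% and <5.7% are derived by dichotomizing the imputed Week 52 HbA1c data sets already created for the primary and key secondary analyses.
- Weight loss ≥5%, ≥10% and ≥15% are derived in the same way from the imputed Week 52 weight data sets, dividing imputed change by baseline weight.
- Each imputed data set is analysed with the logistic model that Table GPGH.6.2 already indicates, and results are pooled by Rubin's rules.
- The complete-case analysis is kept as a sensitivity analysis.

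No new imputation model is needed. Within each imputed data set every patient at or below 6.5% is also below 7.0%, so the pooled proportions stay in order. The cost is SAP wording, a little programming, and possibly slightly lower reported response rates.

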**Table GPGH.6.2. Secondary and Exploratory Efficacy Measures Not Controlled for Type 1 Error**

Objective	Relative to the efficacy measure:	Analysis Conducted in a manner similar to:	Additional Information
Secondary Analyses			
QW tirzepatide 5 mg, 10 mg, and/or 15 mg is superior to insulin degludec at 52 weeks	Change from baseline in fasting serum glucose (central lab)	6.12.1	Use baseline HbA1c strata as a fixed effect in place of baseline HbA1c as a covariate. LSM estimates will be plotted by treatment and visit.
	Proportion of patients achieving an HbA1c target value of $\leq 6.5\%$ (48 mmol/mol)	6.12.2.3	None
	Proportion of patients achieving an HbA1c target value of $< 5.7\%$ (39 mmol/mol).	6.12.2.3	None
	Change from baseline in 7-point SMBG profiles	6.12.1	Use baseline HbA1c strata as a fixed effect in place of baseline HbA1c as a covariate. Use baseline SMBG as a covariate. LSM estimates at 52-weeks will be plotted by treatment and 7-points. In addition to the analyses on each of the 7-points, similar analyses will be done for the 2-hour morning, midday, and evening meal excursions, the mean of all meals 2-hour excursion, the mean of all 7-point measurements, the mean of all pre-meal measurements, and the mean of all 2-hour postprandial measurements.
	Proportion of patients achieving weight loss from baseline of $\geq 5\%$ .	6.12.2.3	Use baseline HbA1c strata as a fixed effect in place of baseline HbA1c as a covariate. Use baseline weight as a covariate.
	Proportion of patients achieving weight loss from baseline of $\geq 10\%$ .	6.12.2.3	Use baseline HbA1c strata as a fixed effect in place of baseline HbA1c as a covariate. Use baseline weight as a covariate.

## Secondary and Exploratory Efficacy Measures Not Controlled for Type 1 Error

Objective	Relative to the efficacy measure:	Analysis Conducted in a manner similar to:	Additional Information
	Proportion of patients achieving weight loss from baseline of $\geq 15\%$ .	6.12.2.3	Use baseline HbA1c strata as a fixed effect in place of baseline HbA1c as a covariate. Use baseline weight as a covariate.
To compare tirzepatide 5 mg, 10 mg, and 15 mg to insulin degludec at 52 weeks	The various Diabetes Treatment Satisfaction Questionnaire change (DTSQc) scores (see Section 6.17.4 for more details).	6.12.1.2	Use baseline HbA1c strata as a fixed effect in place of baseline HbA1c as a covariate. Use baseline DTSQs score as a covariate.
	Changes from baseline in the Impact of Weight on Self-Perceptions Questionnaire (IW-SP) scores.	6.12.1.2	Use baseline HbA1c strata as a fixed effect in place of baseline HbA1c as a covariate. Use baseline IW-SP score as a covariate.
	Changes from baseline in the Ability to Perform Physical Activities of Daily Living (APPADL) scores.	6.12.1.2	Use baseline HbA1c strata as a fixed effect in place of baseline HbA1c as a covariate. Use baseline APPADL score as a covariate.
Exploratory Analyses			
To compare tirzepatide 5 mg, 10 mg, and 15 mg with insulin degludec for the following:	Change from baseline in lipid parameters (total cholesterol, HDL, VLDL, TG).	6.12.1	Use baseline HbA1c strata as a fixed effect in place of baseline HbA1c as a covariate. Use corresponding baseline lipid parameter as a covariate.
	Change from baseline in BMI.	6.12.1	Use baseline HbA1c strata as a fixed effect in place of baseline HbA1c as a covariate. Use corresponding baseline BMI as a covariate.
	Change from baseline in waist circumference.	6.12.1	Use baseline HbA1c strata as a fixed effect in place of baseline HbA1c as a covariate. Use corresponding baseline waist circumference as a covariate.
	Changes from baseline in the European Quality of Life – 5 dimensions (EQ-5D) index and visual analog scale (VAS) scores.	6.12.1.2	Use baseline HbA1c strata as a fixed effect in place of baseline HbA1c as a covariate. Use baseline EQ-5D score as a covariate.
To compare tirzepatide 5 mg, 10 mg, and 15 mg with insulin degludec for the following:	Proportion of patients achieving an HbA1c target $< 6.5\%$ , without weight gain ( $< 0.1$ kg), and without documented symptomatic hypoglycemia or severe hypoglycemia	6.12.2.3	Include the rate of hypoglycemic events at baseline and baseline body weight as additional covariates

## Secondary and Exploratory Efficacy Measures Not Controlled for Type 1 Error

Objective	Relative to the efficacy measure:	Analysis Conducted in a manner similar to:	Additional Information
	Proportion of patients achieving an HbA1c target <7.0%, without weight gain (<0.1 kg), and without documented symptomatic hypoglycemia or severe hypoglycemia	6.12.2.3	Include the rate of hypoglycemic events at baseline and baseline body weight as additional covariates
	Proportion of patients achieving an HbA1c target <6.5%, without weight gain (<0.1 kg), and without clinically significant documented symptomatic hypoglycemia or severe hypoglycemia	6.12.2.3	Include the rate of hypoglycemic events at baseline and baseline body weight as additional covariates
	Proportion of patients achieving an HbA1c target <7.0%, without weight gain (<0.1 kg), and without clinically significant documented symptomatic hypoglycemia or severe hypoglycemia	6.12.2.3	Include the rate of hypoglycemic events at baseline and baseline body weight as additional covariates

Abbreviations: HbA1c = hemoglobin A1c; QW = once-weekly.

### 6.13. Safety Analyses

Unless specified otherwise, safety assessments will be based on the SS ([Table GPGH.6.1](#)). All events that occur between the date of first dose of study drug to the date of patient's safety follow-up visit or patient's end of study participation will be included, regardless of the adherence to study drug or initiation of rescue therapy. For assessing the benefit and risk profile through 52 weeks, selected safety analyses will be conducted by utilizing safety data from first dose through the date of the 52-week visit. Some safety analyses may be conducted after excluding data after the initiation of new antihyperglycemic therapy.

The statistical assessment of homogeneity of the distribution of categorical safety responses among treatment arms will be conducted using Fisher's exact test, unless specified otherwise.

The mean change from baseline differences among treatments at all scheduled visits will be assessed via an MMRM using REML, unless specified otherwise. The model will include country/pooled country, baseline HbA1c ( $\leq 8.5\%$ ,  $> 8.5\%$  [ $\leq 69$ ,  $> 69$  mmol/mol]), baseline concomitant oral antihyperglycemic medication, treatment group, visit and treatment-by-visit

interaction as fixed effects, and baseline value of the safety parameter as a covariate. To model the covariance structure within patients, the unstructured covariance matrix will be used. If this model fails to converge, the covariance structures specified in Section 6.12.1.1 will be tested in order.

For selected safety parameters, time-to-first-event analysis via the cox-proportional hazards model may be conducted. Patients without the event will be censored at the end of study participation. For patients experiencing the event, the “time-to-first-event” will be the time (in days) from first dose to first occurrence of the event.

Where necessary, the rate of events will be analyzed using a generalized linear mixed-effects model assuming the number of events follow a negative binomial distribution and with treatment as a fixed effect. The logarithm of days during the active treatment period will be adjusted as an offset to account for possible unequal treatment duration of follow-up between patients.

